3.3.9.4 Anastrozole

Anastrozole is another third generation nonsteroidal aromatase inhibitor that – similar to letrozole - competitively and reversibly binds to the aromatase enzyme and is approved for treatment of primary and metastatic hormone-receptor positive breast cancer in both pre and post-menopausal women. Anastrozole has been shown to significantly prolong disease-free survival and time-to-recurrence as compared to tamoxifen in a large international double blind randomized phase III study (ATAC-study, Howell et al. 2005). In another large phase III study, anastrozole was compared to letrozole in postmenopausal patients with metastatic breast cancer that had progressed on tamoxifen. There were no significant differences between these two nonsteroidal aromatase inhibitors with regard to the primary endpoint time to progression or other efficacy measures, with the exception of overall response rate that was significantly higher for letrozole (Rose et al. 2003). In a randomized, open-label phase II trial anastrozole was compared to exemestane in patients with locally advanced or metastatic breast cancer. There were no statistically significant differences with regard to overall response rate, clinical benefit rate and time to progression, but the anastrozole group had numerically higher overall response and clinical benefit rates, as well as numerically longer median times to progression (Lombart-Cussac et al. 2012).

Combination Everolimus/Ribociclib plus Anastrozole

The combination of anastrozole plus everolimus/ribociclib has not been evaluated in a clinical study, but the similarity of the mechanism of aromatase inhibition between anastrozole and letrozole and the good clinical efficacy

data for anastrozole (equal to or even favourable when compared to exemestane or letrozole) justify the use of the combined treatment with everolimus and anastrozole as an alternative option in this study.

3.3.9.5 Fulvestrant

Fulvestrant is approved for the treatment of HR+ metastatic breast cancer in postmenopausal women with disease progression following anti-estrogen therapy (USA, Europe). However, also in postmenopausal women without symptomatic visceral disease also after recurrence or progression to an AI, current clinical practice and treatment guidelines include Fulvestrant as treatment option.

In postmenopausal patients who experienced progression after prior endocrine therapy (either AI or tamoxifen), fulvestrant 500 mg emerged as the optimal dose based on the results of the CONFIRM study, which showed that the higher dose (500 mg monthly) significantly prolonged PFS compared to the 250 mg dose. More specifically, subgroup analyses showed that PFS was prolonged in patients who had recurred during anti-estrogen therapy or during AI therapy although not reaching statistical significance for the latter. Median OS was 26,4 months for fulvestrant 500 mg and 22,3 months for 250 mg, irrespective of type of prior endocrine treatment.

Recently, data have been presented for the phase II randomized study (FIRST) of fulvestrant 500 mg compared to anastrozole as a first-line therapy in postmenopausal women with HR+ advanced breast cancer who received no prior endocrine therapy for advanced disease. The observed clinical benefit rate was 72,5 % for fulvestrant vs 67% for anastrozole. No significant difference was observed in ORR. The median Time to Progression (TTP) was significantly longer for fulvestrant than anastrozole.

Paloma-3 is a phase III trial that evaluated clinical efficacy and safety of the CDK4/6 inhibitor palbociclib in combination with fulvestrant. Fulvestrant plus palbociclib was associated with significant and consistent improvement in progression-free survival compared with fulvestrant plus placebo, irrespective of the degree of endocrine resistance, hormone-receptor expression level, and PIK3CA mutational status. The combination could be considered as a therapeutic option for patients with recurrent hormone-receptor-positive, HER2-negative metastatic breast cancer that has progressed on previous endocrine therapy.

3.4 Eribulin

3.4.1 Name, Chemical and Physical Information

HALAVEN 0.44 mg/ml solution for injection is a clear, colourless aqueous solution. One ml contains eribulin mesilate equivalent to 0.44 mg eribulin. Each 2 ml vial contains eribulin mesilate equivalent to 0.88 mg eribulin. This medicinal product contains small amounts of ethanol (alcohol), less than 100 mg per dose as well as water (for injections), hydrochloric acid (for pH-adjustment) and sodium hydroxide (for pH-adjustment).

3.4.2 Chemical Structure

[figure not shown]

Figure 8: chemical structure of eribulin

3.4.3 Mechanism of Action

Eribulin is a non-taxane, microtubule dynamics inhibitor belonging to the halichondrin class of antineoplastic agents. It is a structurally simplified synthetic analogue of halichondrin B, a natural product isolated from the marine sponge *Halichondria okadae*.

Eribulin inhibits the growth phase of microtubules without affecting the shortening phase and sequesters tubulin into non-productive aggregates. Eribulin exerts its effects via a tubulin-based antimetabolic mechanism leading to

G2/M cell-cycle block, disruption of mitotic spindles, and, ultimately, apoptotic cell death after prolonged mitotic blockage.

3.4.4 Experimental Non-clinical Data

Eribulin was not mutagenic *in vitro* in the bacterial reverse mutation assay (Ames test). Eribulin was positive in the mouse lymphoma mutagenesis assay and was clastogenic in the *in vivo* rat micronucleus assay.

No carcinogenicity studies have been conducted with eribulin. An embryofetal development study in rat confirmed the developmental toxicity and teratogenic potential of eribulin. Pregnant rats were treated with eribulin mesilate equivalent to 0.009, 0.027, 0.088 and 0.133 mg/kg eribulin at gestation days 8, 10 and 12. Dose related increased number of resorptions and decreased foetal weight were observed at doses \geq 0.088 mg/kg and increased incidence of malformations (absence of lower jaw, tongue, stomach and spleen) was recorded at 0.133 mg/kg.

3.4.5 Eribulin Pharmacokinetics and Pharmacodynamics

Distribution

The pharmacokinetics of eribulin are characterized by a rapid distribution phase followed by a prolonged elimination phase, with a mean terminal half-life of approximately 40 h. It has a large volume of distribution (range of means 43 to 114 l/m²). Eribulin is weakly bound to plasma proteins. The plasma protein binding of eribulin (100-1000 ng/ml) ranged from 49% to 65% in human plasma.

Biotransformation

Unchanged eribulin was the major circulating species in plasma following administration of Ceribulin to patients. Metabolite concentrations represented <0.6% of parent compound, confirming that there are no major human metabolites of eribulin.

Elimination

Eribulin has a low clearance (range of means 1.16 to 2.42 l/h/m²). No significant accumulation of eribulin is observed on weekly administration. The pharmacokinetic properties are not dose or time dependent in the range of eribulin doses of 0.22 to 3.53 mg/m².

Eribulin is eliminated primarily by biliary excretion. The transport protein involved in the excretion is presently unknown. Preclinical studies indicate that eribulin is transported by P-glycoprotein (Pgp). However, it is unknown whether Pgp is contributing to the biliary excretion of eribulin.

After administration of ¹⁴C-eribulin to patients, approximately 82% of the dose was eliminated in faeces and 9% in urine indicating that renal clearance is not a significant route of eribulin elimination. Unchanged eribulin represented most of the total radioactivity in faeces and urine. Eribulin is mainly (up to 70%) eliminated through biliary excretion. The transport protein involved in this process is unknown. Complete inhibition of the transport could in theory give rise to a more than 3-fold increase in plasma concentrations. It is not recommended to use substances which are inhibitors of hepatic transport proteins such as organic anion-transporting proteins (OATPs), Pgp, multi-drug resistant proteins (MRPs) etc concomitantly with eribulin. Inhibitors of such transporters include but are not limited to: cyclosporine, ritonavir, saquinavir, lopinavir and certain other protease inhibitors, efavirenz, emtricitabine, verapamil, clarithromycin, quinine, quinidine, disopyramide etc. It cannot be excluded that concomitant treatment with inducing substances, such as carbamazepine, phenytoin, St John's wort (*Hypericum perforatum*), could give rise to reduced plasma concentrations of eribulin, and co-administration with inducers should be carried out with caution considering a potential risk for reduced drug efficacy. No marked effects on eribulin exposure (AUC and C_{max}) were observed during treatment with the CYP3A4 inducer rifampicin. However, rifampicin may due to its transporter inhibitory property counteract its possible inducing effect on eribulin elimination. Therefore, the effect of rifampicin may not presently be extrapolated to other inducers.

No drug-drug interactions are expected with CYP3A4 inhibitors. Eribulin exposure (AUC and C_{max}) was unaffected by ketoconazole, a CYP3A4 inhibitor.

Effects of eribulin on the pharmacokinetics of other drugs

Eribulin may inhibit the important drug metabolising enzyme CYP3A4. This is indicated by *in vitro* data and no *in vivo* data is available. Concomitant use with substances that are mainly metabolised by CYP3A4 should be made with caution and it is recommended that the patient is closely monitored for adverse effects due to increased plasma concentrations of the concomitantly used substance. If the substance has a narrow therapeutic range, concomitant use should be avoided. Eribulin does not inhibit the CYP enzymes CYP1A2, 2B6, 2C8, 2C9, 2C19, 2D6 or 2E1 at relevant clinical concentrations.

3.4.6 Safety

Haematology

Myelosuppression is dose dependent and primarily manifested as neutropenia. Monitoring of complete blood counts should be performed on all patients prior to each dose of eribulin. Treatment with eribulin should only be initiated in patients with ANC values $\geq 1500/\mu\text{l}$ and platelets $> 100000/\mu\text{l}$.

Febrile neutropenia occurred in $< 5\%$ of breast cancer patients treated with eribulin. Patients experiencing febrile neutropenia, severe neutropenia or thrombocytopenia, should be treated according to the recommendations in section 8.3.2.

Patients with ALT or AST $> 3 \times \text{ULN}$ experienced a higher incidence of Grade 4 neutropenia and febrile neutropenia. Although data are limited, patients with bilirubin $> 1.5 \times \text{ULN}$ also have a higher incidence of Grade 4 neutropenia and febrile neutropenia. Severe neutropenia may be managed by the use of G-CSF or equivalent at the physician's discretion in accordance with relevant guidelines.

Disseminated intravascular coagulation

Cases of disseminated intravascular coagulation have been reported, typically in association with neutropenia and/or sepsis.

Peripheral neuropathy

Patients should be closely monitored for signs of peripheral motor and sensory neuropathy. The development of severe peripheral neurotoxicity requires a delay or reduction of dose (see section 8.2.2)

In clinical trials, patients with pre-existing neuropathy greater than Grade 2 were excluded. However, patients with pre-existing neuropathy Grade 1 or 2 were no more likely to develop new or worsening symptoms than those who entered the study without the condition.

QT prolongation

In an uncontrolled open-label ECG study in 26 patients, QT prolongation was observed on Day 8, independent of eribulin concentration, with no QT prolongation observed on Day 1. ECG monitoring is recommended if therapy is initiated in patients with congestive heart failure, bradyarrhythmias, medicinal products known to prolong the QT interval, including Class Ia and III antiarrhythmics, and electrolyte abnormalities. Hypokalemia or hypomagnesaemia should be corrected prior to initiating eribulin and these electrolytes should be monitored periodically during therapy. Eribulin should be avoided in patients with congenital long QT syndrome.

Hepatic impairment

A study evaluated the PK of eribulin in patients with mild (Child-Pugh A; $n=7$) and moderate (Child-Pugh B; $n=4$) hepatic impairment due to liver metastases. Compared to patients with normal hepatic function ($n=6$), eribulin exposure increased 1.8-fold and 3-fold in patients with mild and moderate hepatic impairment, respectively. Administration of eribulin at a dose of 0.97 mg/m^2 to patients with mild hepatic impairment and 0.62 mg/m^2 to patients with moderate hepatic impairment resulted in a somewhat higher exposure than after a dose of 1.23 mg/m^2 to patients with normal hepatic function. Eribulin was not studied in patients with severe hepatic impairment (Child-Pugh C). There is no study in patients with hepatic impairment due to cirrhosis.

Renal impairment

A study in patients with different degrees of impaired renal function showed that the exposure of eribulin in patients with moderate renal function (creatinine clearance ≥ 40 to 59 ml/min , $n=6$) was similar to patients with normal renal function while the exposure in patients with severe impairment was increased by 75% (creatinine clearance $< 40 \text{ ml/min}$, $n=4$).

Elderly population

In studies of 1,222 patients treated with eribulin, 244 patients (20.0%) were $> 65 - 75$ years of age and 66 patients (5.4%) were > 75 years of age. Among the 827 of these patients who received the recommended dose of eribulin in the Phase 2/3 breast cancer studies, 121 patients (14.6%) were $> 65 - 75$ years of age and 17 patients (2.1%) were > 75 years of age. The safety profile of eribulin in elderly patients (> 65 years of age) was similar to that of patients ≤ 65 years of age. No dose adjustments are recommended for the elderly population.

Pregnancy

There are no data from the use of eribulin in pregnant women. Eribulin is embryotoxic, foetotoxic and teratogenic in rats. Eribulin should not be used during pregnancy and women of childbearing potential must be advised to avoid becoming pregnant whilst they are receiving eribulin by using effective contraception during and up to 3 months after treatment.

For the most up to date safety information, please refer to the most current edition of the Investigator's Brochure.

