
Both cohorts:
 
 • Indication for an endocrine therapy (Histological confirmation of estrogen receptor positive (ER+) and/or progesterone receptor positive (PgR+) breast cancer). • Up to two lines of previous cytostatic treatment for MBC. • Any endocrine therapy in the history is allowed. • Disease progression following prior treatment with endocrine therapy (endocrine therapy does not have to be the last therapy before inclusion in the trial). • Postmenopausal women. The investigator must confirm postmenopausal status 
 Postmenopausal status is defined either by 
 - Age ≥ 55 years and one year or more of amenorrhea - Age < 55 years and one year or more of amenorrhea and postmenopausal levels of FSH and LH - Prior hysterectomy and has postmenopausal levels of FSH and LH - Surgical menopause with bilateral oophorectomy • Everolimus cohort: • Cholesterol $\leq 2.0 \times \text{ULN}$ • Ribociclib cohort: • Standard 12-lead ECG values assessed by the local laboratory: 	
 • Either hormone-receptor negative MBC or hormone-receptor positive MBC with indication for chemotherapy • Up to three previous chemotherapy treatment lines for metastatic disease • In case of patients of child bearing potential: 
 - Negative pregnancy test (minimum sensitivity 25IU/L or equivalent units of HCG) within 7 days prior to recruitment - Contraception by means of a reliable method (i.e. non-hormonal contraception, IUD, a double barrier method, vasectomy of the sexual partner, complete sexual abstinence). Patient must consent in maintaining such contraception until 3 months after completion of study treatment

- - QTcF interval at screening < 450 msec (using Fridericia's correction)
- - Resting heart rate 50-90 bpm
- - INR \leq 1,5 (ribociclib cohort)
- - Patients must have the following laboratory values within normal limits or corrected to within normal limits with supplements before the first dose of study medication:
 - -Sodium
 - -Potassium
 - -Total calcium

Exclusion Criteria

In General for both study cohorts

1. Treatment with other investigational agents of any type or anticancer therapy during the trial, within 2 weeks prior to the start of treatment.
2. Adverse events due to prior anticancer therapy which are > Grade 1 (NCI CTCAE) and therapeutically relevant at time of treatment start.

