
 • Any endocrine therapy in the history is allowed. • Disease progression following prior treatment with endocrine therapy (endocrine therapy does not have to be the last therapy before inclusion in the trial). • Postmenopausal women. The investigator must confirm postmenopausal status Postmenopausal status is defined either by 
 - Age \geq 55 years and one year or more of amenorrhea - Age $<$ 55 years and one year or more of amenorrhea and postmenopausal levels of FSH and LH - Prior hysterectomy and has postmenopausal levels of FSH and LH - Surgical menopause with bilateral oophorectomy 
Everolimus cohort:
 
 • Cholesterol \leq 2.0 \times ULN 
Ribociclib cohort:
 
 • Standard 12-lead ECG values assessed by the local laboratory: 
 - QTcF interval at screening $<$ 450 msec (using Fridericia's correction) - Resting heart rate 50-90 bpm • INR \leq 1,5 (ribociclib cohort) • Patients must have the following laboratory values within normal limits or corrected to within normal limits with supplements before the first dose of study medication: 
 -Sodium -Potassium -Total calcium 	
 - Negative pregnancy test (minimum sensitivity 25IU/L or equivalent units of HCG) within 7 days prior to recruitment - Contraception by means of a reliable method (i.e. non-hormonal contraception, IUD, a double barrier method, vasectomy of the sexual partner, complete sexual abstinence). Patient must consent in maintaining such contraception until 3 months after completion of study treatment
---	---

Ineligibility Criteria

Patients who fulfill any of the following criteria are not eligible for recruitment:

Exclusion Criteria	
In General for both study cohorts	
Treatment with other investigational agents of any type or anticancer therapy during the trial, within 2 weeks prior to the start of treatment.	
1. Adverse events due to prior anticancer therapy which are > Grade 1 (NCI CTCAE) and therapeutically relevant at time of treatment start.	
2. Known HIV infection.	

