3. Current active hepatitis B or C, clinically relevant known liver dysfunction, e.g. according to Child Pugh Classification class B and C, or biliary disease (with exception of patients with Gilbert's syndrome, asymptomatic gall-stones, liver metastases or stable chronic non-viral liver disease per investigator assessment).	
4. Concurrent disease or condition that might interfere with adequate assessment or evaluation of study data, or any medical disorder that would make the patient's participation unreasonably hazardous.	
5. Other malignant diseases within the last 3 years (apart from carcinoma in situ of the cervix or non-melanoma skin cancer)	
6. Dementia, altered mental status, or any psychiatric or social condition which would prohibit the understanding or rendering of informed consent or which might interfere with the patient's adherence to the protocol.	
7. Life expectancy < 3 months.	
8. Male gender.	
Everolimus/ribociclib cohort (DIVa)	Eribulin cohort (DIVb)

• Known hypersensitivity to any of the excipients of ribociclib, everolimus or any of the other given drugs.• Known hypersensitivity to lecithin (soya) and peanuts (ribociclib-cohort)• Disease or condition, which might restrain the ability to take or resorb oral medication. This includes malabsorption syndrome, requirement for intravenous (IV) alimentation, prior surgical procedures affecting absorption (for example resection of small bowel or stomach), uncontrolled inflammatory GI disease (e.g., Crohn's disease, ulcerative colitis) and any other diseases significantly affecting gastrointestinal function as well as inability to swallow and retain oral medication for any other reason.	
• History of hypersensitivity reactions attributed to eribulin.• Pre-existing neuropathy grade 3 or higher.• Severe Congenital long QT syndrome.• Pregnancy or nursing.

There will be NO EXCEPTIONS to eligibility requirements at the time of recruitment into the study. Questions about eligibility criteria should be addressed PRIOR to requesting recruitment.

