The eligibility criteria for this study have been carefully considered. Eligibility criteria are standards used to ensure that patients who enter this study are medically appropriate candidates for this therapy. For the safety of the patients, as well as to ensure that the results of this study can be useful for making treatment decisions regarding other patients with similar diseases, it is important that no exceptions are made to these criteria for admission to the study.

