4. Aktive Hepatitis B oder C, Einschränkung der Leberfunktion nach der Child Pugh Klassifikation (Grad B und C) oder aktuelle Leber- oder Gallenwegserkrankung (mit Ausnahme von Patientinnen mit Gilberts-Syndrom, mit asymptomatischen Gallensteinen, Lebermetastasen oder stabiler chronischer Lebererkrankung).
5. Vorliegen einer Erkrankung, die die adäquate Einschätzung oder Evaluation der Studiendaten stören könnte, oder Vorliegen anderer Gründe, bei denen die Patientin durch eine Studienteilnahme unverhältnismäßig gefährdet wird.
6. Zweitkarzinom in den letzten 3 Jahre (außer in-situ-Karzinom der Cervix uteri oder Basaliom der Haut).
7. Demenz, veränderter mentaler Status oder andere psychiatrische oder soziale Einflüsse, die das Verständnis der informierten Einwilligung oder welche die Einhaltung des Studienprotokolls verhindern.
8. Lebenserwartung $<$ 3 Monate.
9. Männliche Patienten.

Everolimus/Ribociclib Kohorte (DIVa)	Eribulin Kohorte (DIVb)

 • Anamnestisch bekannte Überempfindlichkeit gegenüber Everolimus/Ribociclib oder chemisch verwandten Substanzen • Unverträglichkeit gegen Soyalecithin und Erdnüsse (Ribociclib-Kohorte). • Unfähigkeit der oralen Aufnahme der Studienmedikation (z.B. bei Malabsorptionssyndrom, parenteraler Ernährung, vorangegangenen chirurgischen Eingriffen, die die Absorption beeinflussen (z.B. Dünndarm- oder Magenresektionen), oder bei unzureichend therapierten entzündlichen Darmerkrankungen (z.B. M. Crohn, Colitis ulcerosa). 	
 • Anamnestisch bekannte Überempfindlichkeit gegenüber Eribulin. • Vorbestehende Neuropathie größer Grad 2. • Schweres kongenitales Long-QT-Syndrom. • Schwangerschaft oder Stillzeit.

Behandlung und Dosierung

Therapie mit Everolimus in Kombination mit einer endokrinen Standardtherapie (DIVa):

Die Indikation zur endokrinen Therapie erfolgt gemäß den Empfehlungen der Arbeitsgemeinschaft Gynäkologische Onkologie (AGO). Die individuelle Therapieentscheidung erfolgt nach Ermessen des verantwortlichen Prüfarztes unabhängig von der klinischen Studie.

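### Section 3.4.6 advises against eribulin in any congenital long QT syndrome, but the eribulin exclusion criterion bars only an undefined severe form

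*Protocol*

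**What the plan says.** The paragraph on QT prolongation in Section 3.4.6 reports that, in an uncontrolled ECG study of 26 patients, prolongation appeared on Day 8 and not on Day 1. It recommends ECG monitoring for certain risk groups and ends: "Eribulin should be avoided in patients with congenital long QT syndrome". No degree of severity is mentioned.

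The exclusion list for the eribulin cohort names the condition in three places, each time with a qualifier:

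- Synopsis, Exclusion Criteria, and Section 5.1, Ineligibility Criteria: "Severe Congenital long QT syndrome".
- Appendix I, German synopsis: "Schweres kongenitales Long-QT-Syndrom".

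No definition of the qualifier is given, either as a QTc value or as a clinical description.

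The only numerical QTc limit at entry, "QTcF interval at screening < 450 msec", stands among the ribociclib criteria. For all cohorts there is a general exclusion for any disorder that would make "participation unreasonably hazardous". Section 5.1 also states the purpose of the list, "Eligibility criteria are standards used to ensure that patients who enter this study are medically appropriate candidates for this therapy", and its force: "There will be NO EXCEPTIONS to eligibility requirements at the time of recruitment into the study".

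**The concern.** The drug section and the eligibility list give different answers for the same patient. A woman with known congenital long QT syndrome that her site does not class as severe falls within the advice to avoid eribulin, yet she meets no eribulin-specific exclusion. Because the qualifier is undefined, two sites could also classify the same patient differently.

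What is at stake is the safety of a small group and the uniform application of an entry criterion. A criterion that names only the severe form also invites the reading that milder forms were considered and accepted, which Section 3.4.6 does not say.

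**Working it through.** No arithmetic underlies this point and the plan gives no figure to reproduce. The check sets the texts side by side and asks whether anything else in the protocol closes the gap.

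**Step 1. The two texts.**

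| Place | Patients covered | Force |
|---|---|---|
| Section 3.4.6 | All congenital long QT syndrome | Advisory: should be avoided |
| Synopsis, Section 5.1, Appendix I (eribulin exclusion) | Severe form only, undefined | Absolute bar, no exceptions |

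The three copies of the criterion agree with one another. The mismatch is between them and Section 3.4.6. It leaves one group uncovered by the specific criterion: congenital long QT syndrome not classed as severe.

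**Step 2. Other safeguards for that group.**

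- *QTc limit at entry.* There is none for eribulin. The 450 msec limit is confined to ribociclib.
- *Baseline ECG.* Table 12 in Section 6.3 requires a 12-lead ECG within 3 weeks before recruitment, with no restriction by cohort. A site would therefore have a tracing, but no eribulin criterion says what finding excludes the patient.
- *ECG on treatment.* The synopsis and Section 9.1 schedule the control-visit ECG for the ribociclib cohort. The next scheduled ECG for an eribulin patient is at the conclusion visit. Section 3.4.6 itself places the QT effect at Day 8, after the baseline tracing.
- *Recommended extra monitoring.* The risk groups named in Section 3.4.6 are heart failure, slow rhythms, QT-prolonging drugs and electrolyte abnormalities. Congenital long QT syndrome is not among them, which fits the intention that such patients should not receive the drug.
- *General hazard clause.* It applies to all cohorts and can exclude the patient. It does not name the condition and depends on the investigator's judgement.

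Only the last item can keep her out.

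**Step 3. How other cautions in Section 3.4.6 were carried over.** Pre-existing neuropathy above Grade 2, which earlier trials excluded, appears in Section 5.1 as an exclusion at grade 3 or higher. The neutrophil minimum of 1500/µl is in the entry criteria. Pregnancy is an exclusion. For these items the list matches its source; for long QT it is narrower.

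**Step 4. Scope.** The criterion governs entry to a cohort planned at about 120 patients (Section 15.3). The protocol gives no frequency for the condition, so no count of affected patients can be derived. As a scale only, one such patient would be 1/120 = 0.8% of the planned cohort.

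**The case against.** The strongest reply has three parts.

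First, Section 3.4.6 belongs to the background chapter and its wording is advisory. Advice to avoid a drug and a narrower absolute bar can both be followed, and the no-exceptions rule protects the listed criteria without turning every background caution into one. Bilirubin is an example: Section 3.4.6 reports more severe neutropenia above 1.5 × ULN, yet entry is allowed up to 2.0 × ULN. This stands in part. The two texts are not logically incompatible. The bilirubin passage, however, describes a risk, whereas the long QT sentence says what to do.

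Second, the general hazard clause is itself an exclusion criterion, and a patient who meets any criterion is ineligible. An investigator who knows of the syndrome and has read Section 3.4.6 has good reason to apply it. This also stands, and it makes the gap narrow. What remains is that the outcome rests on individual judgement, next to a specific criterion that points the other way for milder forms.

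Third, a baseline ECG is required in every cohort. That is correct, but no eribulin criterion uses the result.

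A reader might infer that the protocol permits or directs eribulin in patients for whom it is contraindicated. The documents do not support that: the advice in Section 3.4.6 remains in the protocol, and the hazard clause can be applied.

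**Conclusion.** The point holds as a narrow inconsistency in safety wording that should be corrected. The exclusion criterion is narrower than the protocol's own drug advice, its qualifier is undefined, and no other eribulin entry rule or scheduled control-visit ECG covers the difference.

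The number of patients affected is unknown and likely very small. A reader might take the planned cohort of about 120 as the number at risk; it is only the group to which the criterion applies. No endpoint, analysis set or precision statement is involved.

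A reader might also extend the point to the ribociclib laboratory panel, because Table 26 lists magnesium in a row marked for the eribulin cohort only. The documents do not make that an error. Table 26 lists potassium in both the ribociclib-only and the eribulin-only rows, so the marking labels the row and does not bar the test elsewhere. The lists are minimum lists, and the ribociclib QTc rule in Table 22 orders its own magnesium test.

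The conclusion assumes that the sponsor means Section 3.4.6 as written and did not deliberately choose to admit non-severe cases. Nothing in the protocol states such a choice.

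**What to change.** Delete the qualifier (*Severe*; German *Schweres*) from the eribulin exclusion criterion in the synopsis, Section 5.1 and the German synopsis in Appendix I, so that any congenital long QT syndrome excludes and the list matches Section 3.4.6.

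If the sponsor does intend to admit non-severe cases, the alternative is to define the severe form, for example by a QTc threshold, and to reword Section 3.4.6 to agree. Deletion is simpler and safer.

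The cost is a wording amendment of one word in three places, with no new visit, procedure or test. The downside is the possible exclusion of a very few patients. The sample size and the analysis are unchanged.
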